- The Medical Monitor should be contacted if the subject does not meet the discharge criteria after ≥ 4 hours of extended cardiac monitoring (ie, approximately 8 hours after dosing).
- Any subject who requires extended monitoring on Day 1 must return on Day 2 for the second dose and will be re-monitored as on Day 1, including 8-hour Holter recording (refer to Section 9.9.4). Subjects will be discontinued from study treatment if they do not meet the discharge criteria at 4 hours after the second dose on Day 2. For the safety of the subject, extended cardiac monitoring should be continued until the subject meets the discharge criteria (Table 3).
- Subjects experiencing a symptomatic event (eg, chest pain, dizziness, palpitations, lightheadedness, shortness of breath, or syncope) at any time during the 4-hour monitoring period on Day 1 that is not associated with either a reduction in heart rate or clinically relevant change in 12-lead ECG, may be discharged provided they meet the discharge criteria (Table 3), and as deemed appropriate by the Investigator; however, these subjects must return on Day 2 for the second dose and will be re-monitored as on Day 1. These subjects must be discontinued from treatment if they do not meet the discharge criteria at 4 hours after the second dose on Day 2 and extended cardiac monitoring should be continued until the subject meets the discharge criteria (Table 3).

Study Treatment Discontinuation Related to Post-Dose Cardiac Monitoring

A complete list of reasons for study treatment discontinuation is provided in Section 5.1. Reasons for study treatment discontinuation specific to post-dose cardiac monitoring are provided in Table 4. The Medical Monitor should be contacted before discontinuing a subject.

Table 4: Discontinuation of Study Treatment Related to Post-Dose Cardiac Monitoring

Reasons for Study Treatment Discontinuation Related to Post-dose Cardiac Monitoring a

- Subjects who have a cardiovascular treatment-related symptomatic event (eg, chest pain, dizziness, palpitations, lightheadedness, shortness of breath, or syncope) associated with reduction of the heart rate or associated with clinically relevant 12-lead ECG changes at any time during the 4-hour monitoring period on Day 1 or Day 2 (as applicable).
- Subjects who have not met the discharge criteria on Day 1 after ≥ 4 hours of extended monitoring, or Day 2 by 4 hours post-dose.

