3.5. Baseline Variables

Unless otherwise specified, baseline is defined as the last non-missing measurement taken prior to the first dose (including unscheduled assessments). If measurements include time

(except for health-related quality of life instruments), the date/time will be used to define Baseline. Otherwise, only dates will be compared. For health-related quality of life instruments, only the date will be used to derive Baseline. In the case where the last nonmissing measurement and the date of first dose coincide and time is not collected, if the measurement was planned in the protocol to be done prior to the date of first dose, that measurement will be considered in defining Baseline.

Regarding cardiac analyses, for the analysis of hHR endpoints in Section 3.3.2, the last predose hHR as derived by the cardiac central laboratory from Holter recording will be used as the baseline measurement (which may be based on recording from a partial hourly interval; see derivation of hourly timepoint in Section 9.1.7), except in the analysis of time to nadir hHR by baseline ECG HR, where baseline mean heart rate from pre-dose 12-lead ECG will be used.

The following demographic data and Baseline characteristics will be summarized:

- Age on consent (years)
- Sex
- Race
- Ethnicity
- Woman of childbearing potential (Yes or No)
- Height (cm)
- Weight (kg)
- Body mass index (BMI) (kg/m²)
- Alcohol consumption (Yes or No)
- Caffeine consumption (Yes or No)
- Tobacco use (Yes or No)
- Region (North America, Western Europe, Easter Europe, Other)

The following Baseline characteristics related to UC will be summarized:

- Baseline MMS
- Baseline RB subscore
- Baseline SF subscore
- Baseline ES

- Baseline Physician's Global Assessment (PGA)
- Baseline TMS
- Duration of UC (years)
- Any acute exacerbations within past 12 months (Yes, No, Ongoing), including the number of acute exacerbations among those with any acute exacerbation = Yes
- Colonoscopy within past 12 months (Yes or No)
- Surgery for UC (Yes or No), including the number of surgeries
- Hospitalizations for UC (Yes or No), including the number of hospitalizations
- Naïve to biologic or JAK inhibitor therapy (Yes or No) Reported (used for stratification at randomization)
- Naïve to biologic or JAK inhibitor therapy (Yes or No) Actual (medications reported on the eCRF)
- Baseline corticosteroid use (Yes or No) Reported (used for stratification at randomization)

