9.1.4. Definition and Use of Visit Windows in Reporting

All scheduled study visits are defined relative to Study Day 1, the date of first dose. Scheduled visit windows are defined in Clinical Study Protocol APD334-210 Amendment 2.0 Appendix 1: SCHEDULE OF ASSESSMENTS. A windowing convention will be used to determine the analysis visit value for a given measurement and will be applicable for all byvisit summaries and analyses for efficacy and safety data. Refer to Table 9 below for specific visit windows.

Table 9. Analysis Visit Windows for Efficacy and Safety Analyses

For all efficacy (except endoscopy/MI	MS/histology), efficacy-related biomarkers, safety labs and vital
signs	vis/instology), circucy related biomarkers, safety labs and vital
Scheduled Study Visit (Protocol	Analysis Visit Window (Study Day)
Scheduled Day)	
Baseline	≤1
Week 0 (Day 1)	1
Week 0 (Day 2) ^a	2
Week 2 (Day 15 ± 3)	2 to 22, or 3 to 22 ^a
Week 4 (Day 29 ± 3)	23 to 43
Week 8 (Day 57 ± 3)	44 to 71
Week 12 (Day 85 ± 7)	72 to 99
Week 16 (Day 113 ± 7)	100 to 141
Week 24 (Day 169 ± 7)	142 to 197
Week 32 (Day 225 \pm 7)	198 to 253
Week 40 (Day 281 ± 7)	254 to 309
Week 48 (Day 337 ± 7)	310 to 351
Week 52 (Day 365 ± 14)	> 351
	nposite endpoints that include an endoscopy component and/or
	Assessment, health-related quality of life, ECGs, OCT, and PFT
Scheduled Study Visit (Protocol	Analysis Visit Window (Study Day)
Scheduled Day)	
Baseline	≤1
Week 0 (Day 1)	1
Week 0 (Day 2) ^a	2
Week 12 (Day 85 ± 7) ^b	66 to 113 (66 to 141 for assessments impacted by COVID-19
	pandemic, or impacted by the war in Ukraine) ^c
Week 32 (Day 225 ± 7) [PFT only]	198 to 253 (198 to 281 for assessments impacted by COVID-19
	pandemic, or impacted by the war in Ukraine) ^c
	337 to 393 (337 to 421 for assessments impacted by COVID-19
Week 52 (Day 365 \pm 14) ^b	pandemic, or impacted by the war in Ukraine) ^c

a. Applicable only for participants who require extended monitoring on Day 2 for vital signs and ECGs.

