For cardiac remonitoring upon treatment reinitiation after Day 2, as manifested by more than 1 timed measurement in vital signs or electrocardiogram (ECG) parameters on the same collection date of an unscheduled visit, measurements will be mapped to analysis visit of Cardiac Remonitoring 1, Cardiac Remonitoring 2, etc. in the respective analysis dataset. For analysis, each timed measurement will be programmatically assigned to the nearest hourly timepoint (eg, Predose, 1-hour Postdose) based on their relationship to the dosing time on the same day. If the dosing date/time on the same day is missing, the timepoint will remain missing. Once mapped, these timed measurements from cardiac remonitoring visits will not be considered for any other analysis visit.

b Applicable to all Week 12 and Week 52 efficacy endpoints based on any component of Mayo clinic score, such as clinical remission and symptomatic remission.

c Assessments impacted by the COVID 19 pandemic are reported in the Date of Visit eCRF. COVID-19, coronavirus disease 2019; ECG, electrocardiogram; eCRF, electronic case report form; MMS, modified Mayo Score; OCT, optical coherence tomography; PFT, pulmonary function test; RB, rectal bleeding; SF, stool frequency. Assessments impacted by the war in Ukraine are reported in the protocol deviation document.

Windowing will be applied prior to any missing data calculations. The last nonmissing measurement taken prior to Day 1 (including unscheduled assessments) will be labeled as "Baseline". In the case where the last nonmissing measurement and the date of first dose coincide and time is not collected, if the measurement was planned in the protocol to be done prior to the date of first dose, that measurement will be labeled as "Baseline", not "Week 0". Unless stated otherwise, data from all visits including scheduled, unscheduled, and ET visits will be eligible for allocation to an analysis visit. The 2-Week and 4-Week Follow-Up visits will not be included in the visit windows and will be summarized separately without any window applied.

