If two or more measurements for an endpoint fall in a same analysis visit window, the measurement with the date closest to the protocol scheduled visit day will be used in the analysis. If 2 measurements in the same analysis visit window are equidistant from the protocol scheduled visit day, the earlier one will be used in the analysis. If multiple measurements are available on the same day, then the average of the measurements will be used in the analysis, except for laboratory and ECG data where the assessment at the earliest time of the same day will be used. If both central and local assessments of the same ECG or lab test are available on the same day, the central result will take precedence over the local result.

For the overlapping visit windows at Week 12 and Week 8/16, a hierarchical algorithm will be applied as follows: always map to the Week 12 study visit if the study day falls within the visit window of the Week 12 study visit, then assess the other records for the Week 8 or Week 16 study visit. The same algorithm will be used for Week 48 and Week 52, with Week 52 taking priority.

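### The earliest-of-day rule for ECGs mixes timepoints in the Day 1 value/change summary and, if Day 2 is displayed, can pick the ECG before the second dose over Hour 4

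*SAP*

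**What the plan says.** SAP 9.1.4 sets a windowing convention that "will be applicable for all byvisit summaries and analyses for efficacy and safety data". For ECGs, Table 9 gives one window for Study Day 1 and one for Study Day 2, and neither is split by time of day. The Day 2 window carries a footnote: "Applicable only for participants who require extended monitoring on Day 2 for vital signs and ECGs". Unscheduled records may be allocated to an analysis visit. When several fall on the same day, they are averaged, "except for laboratory and ECG data where the assessment at the earliest time of the same day will be used".

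The same section also contains an hourly mapping. It opens "For cardiac remonitoring upon treatment reinitiation after Day 2", and under it "each timed measurement will be programmatically assigned to the nearest hourly timepoint". No equivalent is written for the original first dose or for Day 2.

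SAP 6.3.2.2 summarises quantitative ECG values and changes from Baseline by visit. It plans no ECG summary by timepoint. For vital signs, SAP 6.3.2.4 does plan a Day 1 summary by timepoint.

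Protocol 9.4.2.1, Table 2, schedules a 12-lead ECG before dosing and at Hour 4. It also allows further ECGs before Hour 4 on Day 1 if heart rate falls below 50 bpm or cardiovascular symptoms appear. A participant who needs extended monitoring on Day 1 "must return on Day 2 for the second dose and will be re-monitored as on Day 1".

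**The concern.** The by-visit table is the only planned summary of the size of ECG interval change around the first dose. Protocol 1.3 names first-dose bradycardia and AV block as reported effects of this drug class, so a reader will take the Day 1 row as the result at the scheduled post-dose assessment. Under the rule as written, some participants supply an earlier ECG, and they are those whose heart rate or symptoms prompted it.

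On Day 2 the Hour 4 ECG belongs to the discharge assessment. Under Protocol Table 4, failing the discharge criteria by then ends study treatment. Where a pre-dose ECG exists that day, the rule takes the pre-dose ECG as the Day 2 value and leaves the Hour 4 one out.

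**Working it through.** The plan states no figure to reproduce, so the check applies its rules to the ECG patterns the protocol allows.

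Inputs:
- Baseline (SAP 3.5): "baseline is defined as the last non-missing measurement taken prior to the first dose (including unscheduled assessments"). The Day 1 pre-dose ECG is therefore Baseline and drops out of the Day 1 row. This agrees with the Table 9 Baseline window, which extends to Study Day 1.
- Windows (SAP Table 9): Study Day 1 and Study Day 2, with no timepoint split.
- Same-day selection (SAP 9.1.4): earliest ECG of the day.
- ECG times (Protocol 9.4.2.1): pre-dose and Hour 4, with extra ECGs when clinically indicated. The Hour 1, 2 and 6 times below are illustrative.

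| Participant | Post-Baseline ECGs recorded | Day 1 value | Day 2 value |
|---|---|---|---|
| A. Routine | Day 1 Hour 4 | Hour 4 | none |
| B. For-cause ECG | Day 1 Hours 2 and 4 | Hour 2 (Hour 4 unused) | none |
| C. Extended monitoring | Day 1 Hours 4 and 6; Day 2 pre-dose and Hour 4 | Hour 4 | Pre-dose (Hour 4 unused) |
| D. Extended, no Day 2 pre-dose ECG recorded | Day 1 Hour 4; Day 2 Hour 4 | Hour 4 | Hour 4 |
| E. For-cause ECG, then extended | Day 1 Hours 1 and 4; Day 2 pre-dose and Hour 4 | Hour 1 (Hour 4 unused) | Pre-dose (Hour 4 unused) |

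Rows A and B together show the Day 1 mixing. Rows C and E show the Day 2 selection, and row D shows that it depends on a pre-dose ECG having been recorded.

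Two other selection rules do not change this. Closeness to the scheduled day cannot separate records from the same day. The precedence of central over local readings concerns two readings of the same test and does not choose between timepoints.

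Next, does a Day 2 row exist? Table 9 defines Day 2 as an ECG analysis visit. SAP Table 14, which lists visits for display, goes from Day 1 to Week 2. Table 14 also still lists Week 20, which the version history says is not a scheduled visit, so the table is not fully maintained. A Day 2 row is neither confirmed nor excluded.

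Last, the outputs not affected. SAP 9.1.3 uses all measurements for summaries of abnormalities and worst-case values, which protects AV-block and QT/QTcF outlier incidence. Holter and vital-sign summaries come from other data. First-dose monitoring ECGs are listed in full under 6.3.2.2.

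**The case against.** The strongest reply is that first-dose conduction safety is well covered elsewhere. Holter gives hourly heart rate and centrally flagged AV block, vital signs have a Day 1 table by timepoint, ECG abnormality incidence uses every record, and the monitoring ECGs are listed. ECG intervals are not among the named safety endpoints in Protocol 10.11.1 or SAP 2.2.2. The selection rule is prespecified and the same in both arms, and a for-cause ECG is itself a post-dose record of the triggering event. The output shells, which are not part of the documents, may add a timepoint layout. All of this limits the importance of the point. It does not make the selection right: none of those outputs gives interval change at a defined post-dose time, and a shell that contradicted 9.1.4 would leave the programmers with two instructions.

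A reader might go further in three ways that the documents do not support.

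- All Hour 4 ECGs are lost on Day 1. SAP 9.1.4 does say "The last nonmissing measurement taken prior to Day 1 (including unscheduled assessments) will be labeled as" Baseline. Read literally, that makes the screening ECG Baseline and the Day 1 pre-dose ECG the Day 1 value for everyone. But SAP 3.5 and the Table 9 Baseline window both place the Day 1 pre-dose ECG at Baseline, so this is loose wording. The Day 2 selection is the same under either reading.
- The Day 2 value is an unexposed one. It is not: it precedes the second dose but follows the first.
- The summary is biased in a known direction. The documents give neither the number of ECGs displaced nor how earlier values compare with Hour 4, so no direction or size can be stated. Any numerical range would rest on assumed inputs alone.

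**Conclusion.** The point stands as a minor error in a stated rule. Taken as written, SAP 9.1.4 makes the Day 1 row of the ECG value/change summary a mixture of Hour 4 and earlier post-dose ECGs, with the earlier ones coming from participants who had cardiac findings. It also makes the Day 2 analysis value the ECG before the second dose whenever one was recorded. The Day 2 part has practical effect only if Day 2 is displayed.

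Only the descriptive PR, RR, QRS, QT and QTcF value/change summary changes; no test, endpoint or abnormality count does. The conclusion rests on the SAP 3.5 definition of Baseline and on the shells following the SAP text.

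**What to change.** In SAP 9.1.4, exempt timed Day 1 and Day 2 first-dose-monitoring ECGs from the earliest-of-day rule and apply the nearest-hour mapping already written for re-monitoring after re-initiation. State that the Hour 4 ECG is the Day 1 value, and the Day 2 value where that monitoring was done, in the 6.3.2.2 value/change summary. If Day 2 is to be shown, add it to Table 14.

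As housekeeping, change the Baseline label in 9.1.4 so that it refers to the time before the first dose, not before Day 1, to match SAP 3.5.

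The cost is a few lines of SAP text and the matching programming. The ECGs are already collected.

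### Followed literally, the SAP 9.1.4 window-priority rule moves on-schedule Week 16 and Week 48 rectal bleeding and stool frequency records to Weeks 12 and 52, so attended visits count as nonresponse in the exploratory symptomatic endpoints

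*SAP*

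**What the plan says.** Table 9 in SAP 9.1.4 has two blocks of analysis windows. The first covers efficacy other than endoscopy, MMS and histology, and sets Week 8 at Days 44 to 71, Week 16 at Days 100 to 141 and Week 48 at Days 310 to 351. The second has wider windows: for Week 12, "66 to 113 (66 to 141 for assessments impacted by COVID-19" pandemic or the war in Ukraine), and for Week 52, "337 to 393 (337 to 421 for assessments impacted by COVID-19" or the war). Footnote b makes these wider windows "Applicable to all Week 12 and Week 52 efficacy endpoints based on any component of Mayo clinic score" and names symptomatic remission as an example.

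The text after the table deals with the overlap. The instruction is to "always map to the Week 12 study visit if the study day falls within the visit window of the Week 12 study visit", and "then assess the other records for the Week 8 or Week 16 study visit". It continues: "The same algorithm will be used for Week 48 and Week 52, with Week 52 taking priority". When several records share a window, "the measurement with the date closest to the protocol scheduled visit day will be used in the analysis". Unless stated otherwise, "data from all visits including scheduled, unscheduled, and ET visits will be eligible for allocation to an analysis visit".

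Three other provisions matter:

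- SAP 9.1.3 puts windowing before imputation.
- SAP 5.3.1.1 counts every missing binary outcome as nonresponse, and Table 7 in SAP 6.1 extends this to the exploratory binary endpoints.
- SAP 3.4.1 lists symptomatic remission and symptomatic response at every study visit, including Weeks 16 and 48. Table 6 in Protocol Appendix 1 schedules the stool frequency (SF) and rectal bleeding (RB) subscores at both.

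**The concern.** The first-block windows do not overlap one another, and the second block has no Week 8, 16 or 48 row. The overlap rule can therefore only concern the wide Week 12 and Week 52 windows meeting the first-block windows for Weeks 8, 16 and 48. It governs exactly the RB and SF records behind the symptomatic endpoints.

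The rule is triggered by the study day alone. A Week 16 visit made on its target day is assigned to Week 12, loses there to the real Week 12 record, and is not returned to Week 16. The participant attended and has data but is counted as a nonresponder. The same happens at Week 48.

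What is at stake is the symptomatic time course. Both arms' rates would fall at two of the ten listed visits and the treatment difference would shrink there, for reasons unrelated to the drug.

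**Working it through.** **Inputs.** Target days and visit windows come from Table 6 in Protocol Appendix 1 (Week 8: Day 57 ± 3; Week 16: Day 113 ± 7; Week 48: Day 337 ± 7). Analysis windows come from SAP Table 9.

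**Scheduled days.** Day = 7 × week + 1 gives 85, 113, 337 and 365 for Weeks 12, 16, 48 and 52, as the documents state.

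**Days lost under the literal rule.** Count the days of each protocol window that lie inside a wide window.

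| Visit | Protocol window | Taken by Week 12 or 52 | Days lost | Lost if flagged as COVID-19 or war impacted |
|---|---|---|---|---|
| Week 8 | 54–60 | none (wide window starts at 66) | 0 of 7 | 0 of 7 |
| Week 16 | 106–120 | 106–113 | 8 of 15 | 15 of 15 |
| Week 48 | 330–344 | 337–344 | 8 of 15 | 8 of 15 |

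Both target days are among those lost.

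**Is the moved record used at Week 12 or 52?** A moved Week 16 record is at least 106 − 85 = 21 days from the Week 12 target. A moved Week 48 record is at least 365 − 344 = 21 days from the Week 52 target. An on-schedule record is at most 3 days (Week 12) or 7 days (Week 52) away under the protocol, and at most 7 or 14 days away under the tolerances printed in SAP Table 9. The closest-day rule therefore always prefers the on-schedule record.

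**What is left.** Week 16 keeps a value only if some record falls on Days 114 to 141, and Week 48 only if one falls on Days 310 to 336. Otherwise the visit is empty and is imputed as nonresponse.

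**Effect on reported rates (illustration).** Reported rate = true rate × (1 − share of visits moved), with the same share in both arms and no other record available. The documents give no visit-timing data, so the shares and the true rates of 50% v 30% are assumptions; 53% is 8/15, the share if visits spread evenly over the protocol window.

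| Share moved | Reported rates | Difference (true: 20 points) |
|---|---|---|
| 25% | 37.5% v 22.5% | 15.0 |
| 53% (8/15) | 23.3% v 14.0% | 9.3 |
| 75% | 12.5% v 7.5% | 5.0 |

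**Effect on the mixed models.** The by-visit RB, SF and composite analyses are not imputed (SAP 5.3.2), so they lose records and precision but are not biased by imputation. The standard error at the visit grows by at most 1/√(1 − share): 1.15, 1.46 and 2.00 for the three shares. This is an upper bound because the model borrows from other visits.

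**The case against.** The strongest reply is that the second step of the rule, on the remaining records, can mean records not chosen for Week 12 or 52. On that reading an unselected Day 113 record goes back to Week 16 and nothing is lost. This also fits the fact that the SAP keeps Weeks 16 and 48 as analysis visits and that version 3.0 re-cut the Week 16 window. The reading is possible. It sits less well with the first step, which has no exception and turns on whether the day falls in the window, not on whether the record is selected. The SAP nowhere says that an unselected record returns. Two programmers could follow the text and report different results.

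Other points:

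- Footnote b is confined to Week 12 and Week 52 endpoints. That is true, but it fixes which window the priority rule uses, and the priority rule is what takes the record.
- The heading of the second block is incomplete in the copy reviewed. Footnote b still settles that Mayo-component endpoints are covered.
- The counts assume an RB/SF record carries the visit date. Protocol 9.4.2 and SAP 3.1.1 key these subscores to the visit date when there is no endoscopy, as at Weeks 16 and 48, which supports the assumption. If an earlier diary date were used, the loss would grow at Week 16 and shrink at Week 48.
- The endpoints are exploratory, the rule is blind to treatment, and the effect on the difference is attenuation. All of this stands and limits the weight of the point.

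**Conclusion.** The concern holds. Followed as written, the rule removes 8 of 15 permitted days, including the target day, at each of Weeks 16 and 48. For assessments individually flagged as affected by COVID-19 or the war, it removes all 15 at Week 16. Attended visits are then scored as nonresponse in symptomatic remission and symptomatic response, unless another record falls in the remaining part of the window.

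The day counts follow from the documents. The size of the fall in response rates does not, and the figures above are illustrations only.

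The binary endpoints affected are exploratory, outside the fixed testing sequence and tested at a nominal 5% (SAP 5.1). With on-schedule Week 12 and Week 52 records, the primary and key secondary endpoints are not scored as failures by this route. The matter should be corrected, but it does not threaten the main conclusion of the trial.

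**What to change.** Add one sentence to SAP 9.1.4: the wide Week 12 or Week 52 window claims only the single record selected for that visit (closest to Day 85 or Day 365), and every unselected record, including unscheduled and early-termination records, stays eligible for Weeks 8, 16 and 48 under the first-block windows of Table 9 (Days 44 to 71, 100 to 141 and 310 to 351).

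Where on-schedule Week 12 and Week 52 records exist, this keeps 15 of 15 protocol-window days at both Week 16 and Week 48, because 106 to 120 lies within 100 to 141 and 330 to 344 lies within 310 to 351. The selection for Weeks 12 and 52 does not change. If the Week 12 or Week 52 record is missing, a Day 113 or Day 337 record would still be taken for that visit, as it is now.

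The cost is the sentence and the matching programming. No new data are needed.
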